### 2.2 Analysis sets

For all analysis sets, participants will be analyzed according to the study treatment(s) received.

The safety analysis set will include all participants who received any study drug.

The PK analysis set will include all participants with at least one available valid (i.e., not flagged for exclusion) PK concentration measurement, who received any study drug and with no protocol deviations that impact on PK data.

The PD analysis set will include all participants with available PD data and no protocol deviations with relevant impact on PD data.

The analysis sets and protocol deviation codes are related as [Table 2-1](#).

**Table 2-1 Protocol deviation and analysis sets**

| Category
Deviation code   | Text description of deviation  | Data exclusion                                  |
|--|--|---|
| Subjects are excluded from Safety analysis in case of these PDs:  | 

• Informed consent was not obtained (INCL01)

• Subject did not receive any dose of study drug (TRT10)

  | Exclude subject from Safety analysis set |
| Subjects are excluded from PK analysis in case of these PDs:  | 

• Informed consent was not obtained (INCL01, OTH08)

  | Exclude subject from PK analysis set     |
| Subjects are excluded from PD analysis in case of these PDs:  | 

• Informed consent was not obtained (INCL01).

• Subject did not receive any dose of study drug (TRT10)

• Subject was randomized but the diagnosis of definite or probable IPF with 5 years of the screening visit is not confirmed (inclusion criteria number 3, INCL03)

 | Exclude subject from PD analysis sets    |
| Subjects' visits may be excluded from PD analysis since the following PD occurs:  |  |   |
| 

• Use of prohibited medications which affect PD data (based on the list of prohibited medications provided in section 5.2 of the protocol, COMD01)

 |  |   |

Decisions regarding the exclusion of participants and/or participant data from analyses will be made prior to final database lock (DBL).

### **2.2.1 Subgroup of interest**

Not applicable.

## **2.3 Patient disposition, demographics, and other baseline characteristics**

### **2.3.1 Patient disposition**

The patient disposition will be summarized by cohort and treatment group using safety set.

The number and percent of subjects screened, randomized, completed, and discontinued from the study will be summarized with reasons of discontinuation.

Screened participants, including those who completed screening and were treated, and reasons for not completing the study will be also listed by cohort and participant.

### **2.3.2 Demographics and other baseline characteristics**

Demographic and other baseline data including disease characteristics, including smoking status, , Standard of care (Pirfenidone, Nintedanib, or No treatment), history of other respiratory diseases, history of pulmonary exacerbations, and the number of years of IPF diagnosis will be listed by cohort, treatment group, and patient using the safety analysis set.

Summary statistics will be provided by cohort and treatment group. Categorical data will be presented as frequencies and percentages. For continuous data, mean, standard deviation, median, minimum, and maximum will be presented. For selected parameters, 25th and 75th percentiles will also be presented when applicable.

Relevant medical history, current medical conditions at baseline (summarized by system organ class and preferred term), results of laboratory screens, drug tests and any other relevant information will be listed by cohort, treatment group and patient.

## **2.4 Treatments (study treatment, rescue medication, concomitant therapies, compliance)**

### **2.4.1 Study treatment / compliance**

The safety analysis set will be used for the analyses.

Summary statistics will be provided for treatment compliance by treatment group.

The duration of exposure in weeks to investigational drug will be summarized by means of descriptive statistics.

The use of the standard of care medication (pirfenidone, nintedanib, or no treatment) will be summarized by treatment group.

### **2.4.2 Prior, concomitant and post therapies**

Concomitant medications and significant non-drug therapies prior to and after the start of the study treatment will be summarized according to the Anatomical Therapeutic Chemical (ATC) classification system, by cohort, treatment group, epoch, and patient using safety analysis set.

## **2.5 Analysis supporting primary objective(s)**

The primary aim of the study is to assess the efficacy of the investigational products, compared to placebo in IPF participants. This will be evaluated by assessing change from baseline to end of treatment epoch (26 weeks of treatment) in Forced Vital Capacity (FVC) expressed in percent predicted (FVC%p). Reduction of the decrease in change from baseline is considered a favorable outcome. The primary analysis will be conducted using PD analysis set.

### **2.5.1 Primary endpoint(s)**

The primary endpoint of the study is change from baseline in FVC%p. It will be calculated as:

$FVC\%p \text{ (EoT)} - FVC\%p \text{ (Baseline)}$ .

### **2.5.2 Statistical hypothesis, model, and method of analysis**

The treatment effect of the primary endpoint will be analyzed using a Bayesian random slope model to assess the difference in reduction rate (slope) between the treatment group and placebo group. The statistical model will include the intercept, time (as continuous variable), the interaction of treatment and time, the interaction of baseline FVC%p and time, and the stratification factor for the randomization, standard of care treatment with 2- categories (nintedanib and/or pirfenidone, neither) as fixed effect, and the intercept and slope of time for each participant as random effects. A robust weakly informative prior for the placebo time slope (based on 9 phase II and III studies after 2012 with total of 492 participants) will be used in the Bayesian analysis. The robustified informative prior for the change from baseline in FVC%p is

comprised of 3 components of normal distributed random variables with the following information in terms of weight (W), mean (M), and standard deviation (S):

**Table 2-2 Composition of the robust weakly informative prior for the placebo tie slope**

|   | Comp1 | Comp2 | Comp3 |
|---|-------|-------|-------|
| W | 0.526 | 0.174 | 0.300 |
| M | -2.93 | -2.75 | -3.00 |
| S | 0.865 | 1.837 | 4.754 |

This effectively means that we assume a placebo decline of 3% at week 26 from the baseline for the placebo group is expected. This prior belief is fixed at the design stage. Any new placebo historical data that becomes available, will not be used as part of a prior. The impact of using this placebo prior means that there would be in effect 11 more placebo participants contributing to the data analysis. A non-informative prior will be used for the rest of the parameters, assuming the change from baseline in FVC%p has a normal distribution with mean=0 and a very large SD (e.g., 1E6).

The primary summary measure of interest is the difference in FVC%p between active and placebo at week 26 derived from the Bayesian statistical model as the posterior mean estimation of the treatment effect over placebo for change from baseline FVC %p at the end of treatment (26 weeks). Statistical evidence of treatment effect will be concluded if the probability that the effect is better than placebo by 90% and there is at least 50% probability that the effect over placebo is >1.3%. No adjustments for multiplicity will be applied for this exploratory study.

### **2.5.3 Handling of missing values/censoring/discontinuations**

If a participant who was not on standard of care at randomization initiates treatment with standard of care during the study, the subject's data collected after the initiation of standard of care will be set to missing from the primary analysis. All the missing data are considered as missing at random. No further handling will be conducted.

### **2.5.4 Poolability of the Placebo patients across different cohorts**

Only one cohort was included due to the early termination of the study, therefore no pooling of the Placebo patients across different cohorts will be conducted.

### **2.5.5 Sensitivity analyses**

The study will be early terminated. There will be no sensitivity analyses conducted under this situation.

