12.4.5 Sensitivity analyses

The same Bayesian model stated in [Section 12.4.2](#) will be repeated using non-informative prior for the placebo group. The Bayesian posterior probability of the treatment effect (treatment - placebo) for the statistical evidence stated in [Section 12.4.2](#) will be derived.

If a participant who was not on background therapy at randomization initiates treatment with background therapy during the study, the subject's data collected after the initiation of background therapy will be excluded from the primary analysis. However, a sensitivity analysis that includes the excluded data may be performed.

If a participant discontinues the original background therapy during the treatment period, a protocol deviation will be filled and the data generated from the participant will be included in the formal analysis. A sensitive analysis may be conducted further by excluding these data.

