12.4.6 Supplementary analysis

Frequentist approach of linear mixed model will be conducted to further validate the statistical results from main analysis. The model will include all fixed and random effect stated in [Section 12.4.2](#).

A second mixed model will also be fitted with the interaction of the background therapy category and the treatment in order to assess the treatment effect within each background therapy category.

Subgroup analyses might be conducted to justify the impact on the robustness of the statistical estimate when the situation of participants entering the multiple cohorts occurs. Detailed information will be specified in the statistician analysis plan (SAP).

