### **2.5.6 Supplementary analyses**

There will be no supplementary analyses conducted due to the early termination of the study.

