## **4 Change to protocol specified analyses**

Due to the decision of the early termination of the study, the following analyses will not be performed, therefore removed from the SAP:

1. The pooling of the placebos from different cohorts
2. All sensitivity and supplemental analyses for the primary endpoint
3. All the planned CSR analyses on exploratory objectives and endpoints stated in [Section 1.2](#)
4. Planned Interim Analyses

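### The SAP keeps the informative placebo prior and two-part rule for FVC%p but drops the protocol's flat-prior rerun and frequentist model, so the verdict's dependence on the prior will not be shown

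*SAP*

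**What the plan says.** **Protocol.** Section 12.4.5 states that the primary model "will be repeated using non-informative prior for the placebo group". It adds that "The Bayesian posterior probability of the treatment effect (treatment - placebo) for the statistical evidence stated in" section 12.4.2 will be derived, so the two-part rule itself is to be recomputed. Section 12.4.6 adds: "Frequentist approach of linear mixed model will be conducted to further validate the statistical results from main analysis".

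**SAP, what is kept.** Section 2.5.2 and Table 2-2 retain the three-component mixture prior on the placebo slope. On its meaning, the SAP says "This effectively means that we assume a placebo decline of 3% at week 26 from the baseline for the placebo group is expected", and on its weight, "The impact of using this placebo prior means that there would be in effect 11 more placebo participants contributing to the data analysis". The rule is unchanged: 90% probability that the effect exceeds 0, and at least 50% probability that it exceeds 1.3.

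**SAP, what is dropped.** Section 2.5.5: "There will be no sensitivity analyses conducted under this situation". Section 2.5.6: "There will be no supplementary analyses conducted due to the early termination of the study". Section 4, item 2 lists as removed "All sensitivity and supplemental analyses for the primary endpoint". The reason given is early termination.

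**SAP, what remains without the prior.** Section 2.6.1.1 has an MMRM of FVC in mL with summary statistics, Kaplan-Meier estimates for the progression composite and, if the data allow, logistic comparisons of event rates, in which FVC%p enters only as a decline of at least 10% predicted.

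**The concern.** The rule on FVC%p is the only place where the plan declares statistical evidence of a treatment effect, and it uses outside information about placebo. The protocol paired it with an analysis that shows whether the conclusion survives without that information. The SAP removes the check and keeps the prior-driven conclusion.

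The stated reason explains other deletions. With one cohort there are no placebos to pool, and the interim can no longer take place. It does not explain this one: the rerun needs no further cohort, participant or visit. If termination left fewer placebo participants, the prior would carry more of the placebo estimate and the check would matter more.

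Without it, a reader cannot tell whether a pass or a fail came from the trial's data or from the prior. The mL and event-rate analyses may agree or disagree in direction, but they cannot say whether the rule would be met without the prior.

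**Working it through.** **Inputs.** Prior weights 0.526/0.174/0.300, means -2.93/-2.75/-3.00, SDs 0.865/1.837/4.754 (SAP Table 2-2). Rule: SAP 2.5.2. SD 5, effect 2, 40 evaluable per arm: protocol 12.8.1. Assumed, because the documents do not give them: true placebo declines other than 3, and any final n other than 40.

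**Approximation.** Week-26 arm means with known SD replace the random-slope model. The active arm has a flat prior. With observed placebo mean y and s² = 25/40 = 0.625, each prior component k updates to

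- variance v_k = 1/(1/S_k² + 1/s²)
- mean m_k = v_k(M_k/S_k² + y/s²)
- weight w_k proportional to W_k × Normal(y; M_k, S_k² + s²).

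Then P(effect > c) = Σ w_k Φ[(active mean - m_k - c)/√(v_k + s²)]. With a flat placebo prior, P(effect > c) = Φ[(d - c)/(5√(2/40))] = Φ[(d - c)/1.118], where d is the observed difference.

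**1. The plan's own figure.** Protocol Table 17-5 gives 79% power at effect 2 with 40 per group. With the mixture prior, placebo change -3 and an interim at half the sample under the protocol 12.7.2 rules, simulation gives 79.2%. At effects 1.6/1.8/2.2/2.4 it gives 66.1/73.0/84.6/88.8% (stated 65/72/85/89%). Type I error is 12.0% (stated approximately 13%). A flat prior with the same interim gives 73.1%. The stated power therefore relies on the prior, and the approximation tracks the plan's calculation.

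**2. Single final analysis (the interim is now cancelled), 40 per arm.** The flat-prior columns do not depend on the placebo decline.

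| True placebo decline | Pass, no effect: prior / flat | Pass, effect 2: prior / flat | Verdicts differ, effect 2 | Bias with prior |
|---|---|---|---|---|
| 4 | 4.6% / 10.0% | 63% / 69% | 7.8% | -0.32 |
| 3 | 7.9% / 10.0% | 76% / 69% | 7.7% | -0.03 |
| 2 | 14% / 10.0% | 82% / 69% | 12.9% | +0.27 |
| 1 | 20% / 10.0% | 82% / 69% | 12.2% | +0.44 |

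At decline 3 and effect 2, 9% of passes fail the flat-prior rule. At decline 3 with no effect, 7% of false positives do.

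**3. Observed difference needed to pass.** Flat: 1.2816 × 1.118 = 1.43. With the prior: 1.69, 1.33 and 1.00 at an observed placebo change of -4, -3 and -2.

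**4. Two worked results.**

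- *Placebo -2, difference 1.10 (active -0.90).* Component 1: v = 1/(1/0.748 + 1/0.625) = 0.341 and m = 0.341 × (-3.92 - 3.20) = -2.42. All components: weights 0.698/0.173/0.130, means -2.42/-2.12/-2.03, so the placebo posterior mean is -2.32 and the estimated effect -0.90 + 2.32 = 1.42. P(>0) = 0.915 and P(>1.3) = 0.549: pass. Flat: Φ(1.10/1.118) = 0.837 and Φ(-0.20/1.118) = 0.429: fails both parts.
- *Placebo -4, difference 1.60 (active -2.40).* The placebo posterior mean is -3.63, so the estimated effect is 1.23. P(>0) = 0.884 and P(>1.3) = 0.468: fails both parts. Flat: 0.924 and 0.606: pass.

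**5. Smaller sample.** On the stated worth of 11 participants, the prior's share of placebo information is 11/(11 + 40) = 22% at 40 and 11/(11 + 20) = 35% at an assumed 20. At 20 per arm, decline 3 and effect 2, verdicts differ in 10.6% of trials and 15% of passes fail flat.

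**The case against.** The removal is open. It appears in the document history, dated before database lock, and in SAP 1.2.1, 2.5.5, 2.5.6 and section 4, with a reason each time. The trial is exploratory and non-registrational, and the protocol gives the flat-prior run no decision role. How many secondary checks to report after early termination is partly the sponsor's judgement.

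The prior is also reasonable. It is robustified and fixed at design. At the expected decline of 3 it lowers the false-positive rate (7.9% against 10.0%) and the root mean squared error (0.96 against 1.12). The latter is also lower at declines of 4 and 2 (1.05 and 1.02) and higher only at 1 (1.17). Averaged over the prior itself, the error rate is 10.0%, the same as flat. The 14% and 20% figures need declines that the documents do not support. Discordant verdicts are mostly borderline trials, and the false-positive rate barely changes at 20 per arm. The mL MMRM analyses the same FVC measurement, and if the summary statistics in 2.6.1.1 cover FVC%p, a reader could approximate a flat-prior result.

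All of this stands as a case for keeping the prior in the primary analysis and for treating the issue as moderate. It does not replace the check. Neither the MMRM nor the logistic comparison recomputes the rule. A reader's approximation from summary statistics, if those cover FVC%p at all, is not the random-slope rerun. Borderline results are where the comparison is needed.

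**Conclusion.** The concern holds. The SAP retains a decision rule that depends on an informative placebo prior and removes both analyses that the protocol specified to test that dependence. No model of continuous FVC%p, and no evaluation of the rule, is left without the prior. At the plan's own values the choice of prior changes the verdict in about 1 trial in 13 (7.7%). The direction depends on placebo: the prior makes passing harder when placebo declines by more than expected and easier when it declines by less.

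The omission is read directly from the documents. The sizes rest on week-26 means with known SD 5 in place of the random-slope model, 40 per arm, a single final analysis and, away from 3, assumed placebo declines. The exact thresholds and probabilities should be read as indicative. The final sample size is not stated. This should be fixed; it affects how the result is interpreted and does not make the primary analysis invalid.

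**What to change.** In SAP 2.5.5, reinstate the protocol 12.4.5 rerun of the primary model with a non-informative placebo prior. Report P(effect > 0) and P(effect > 1.3) under both priors side by side, so that any disagreement on the rule is visible. Amend SAP section 4, item 2, and the matching statement in 1.2.1. Restoring the protocol 12.4.6 frequentist mixed model is optional. The prior and the rule stay as they are.

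The cost is one extra run of a model that must be programmed anyway, one table row and a few lines of SAP text, with no new participants, visits or data. The downside for the sponsor is that a positive or negative verdict may be shown to depend on the prior.

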### **2.5.6 Supplementary analyses**

There will be no supplementary analyses conducted due to the early termination of the study.

## 2.6 Analysis supporting secondary objectives

### 2.6.1 Secondary endpoint(s)

Secondary endpoints include efficacy and pharmacodynamic endpoints and safety endpoints ([Table 1-1](#)). The analyses on efficacy and pharmacodynamic endpoints will be conducted using PD analysis set. The analyses on safety endpoints will be conducted using Safety analysis set.

Analysis details will be specified in the following subsequence sections.

#### 2.6.1.1 Efficacy and/or Pharmacodynamic endpoint(s)

##### Efficacy

Change from baseline to end of treatment epoch (26 weeks of treatment) in Forced Vital Capacity (FVC) expressed in mL will be analyzed using a Mixed Effect Model for Repeated Measurement (MMRM) model. The model will include treatment and visit as fixed effects, standard of care treatment (Nintedanib, Pirfenidone, or neither) and baseline value as a covariate, treatment-by-visit and baseline-by-visit as interaction terms. The within subject correlation will be modeled using a repeated statement in SAS Proc Mixed with unstructured covariance matrix. In case of non-convergence the model, an alternative AR(1) covariance may be implemented.

Summary statistics of change from baseline in FVC by visit and treatment will be presented.

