12.4.2 Statistical model, hypothesis, and method of analysis

The treatment effect of the primary endpoint will be analyzed using a Bayesian random slope model to assess the difference in reduction rate (slope) between the treatment group and placebo group. The statistical model will include the intercept, time (as continuous variable), the interaction of treatment and time, the interaction of baseline FVC%p and time,

and the background therapy as fixed effect, and the intercept and slope of time for each participant as random effects. A robust weakly informative prior for the placebo time slope (based on 9 phase II and III studies after 2012 with total of 492 participants) will be used in the Bayesian analysis. The robustified informative prior for the change from baseline in FVC%_p is comprised of 3 components of normal distributed random variables with the following information in terms of weight (W), mean (M), and standard deviation (S):

Table 12-1 Composition of the robust weakly informative prior for the placebo time slope

	Comp1	Comp2	Comp3
W	0.526	0.174	0.300
M	-2.93	-2.75	-3.00
S	0.865	1.837	4.754

By using this prior slope of placebo, a 3% decline at week 26 from the baseline for the placebo group is expected. The impact of using this placebo prior means that there would be in effect 11 more placebo participants contributing to the data analysis. A non-informative prior will be used for the rest of the parameters, assuming the change from baseline in FVC%_p has a normal distribution with mean=0 and a very large SD (e.g. 1.E6). The Bayesian posterior mean estimation of the treatment effect over placebo for change from baseline FVC %_p at the end of treatment (26 weeks) will be derived. Statistical evidence of treatment effect will be concluded if the probability that the effect is better than placebo by 90% and there is at least 50% probability that the effect over placebo is >1.3%. No adjustments for multiplicity will be applied for this exploratory study.

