12.8 Sample size calculation

12.8.1 Primary endpoint(s)

Without considering the drop-off rate, 40 participants per active treatment group and at least 40 participants on placebo of each cohort will give at least 80% power to detect a treatment improvement in change from baseline in FVC%_p (treatment – placebo) for at least 2% in patients with IPF assuming the standard deviation is around 5%.

The sample size calculation is based on the primary efficacy endpoint of change from baseline in FVC%_p at week 26. The criteria for this calculation aimed for a 90% level of proof that difference in change in FVC%_p from baseline to week 26 between treatment and placebo and the mean treatment effect is at least 1.3% better than placebo effect with 50% probability. The former targets proof that the treatment produces a statistically significant improvement in change from baseline in FVC, while the latter targets proof of clinical relevance.

The sample size calculation also takes into account the interim analysis step with futility and early efficacy criteria defined in [Section 12.7](#). The overall type I error at the end of study will be approximately 13%.

Additional participants may be enrolled if more than 15% of the planned randomized participants have not completed the 26 weeks of treatment, as per protocol requirements. Prior to enrolling additional participants, a DMC review of safety data will occur to ensure there are no tolerability/safety issues that would advise against enrolling additional participants.

Refer to [Section 17](#) for cohort specific sample size after considering drop off rate and randomization ratio between the treatment group and placebo group.

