### **Pulmonary physiology**

To assess the impact of the IPs on pulmonary physiology, change from baseline to the end of treatment epoch (26 weeks of treatment) in DLCO and DLCO/Hb ([Brian L. Graham](#)) will be analyzed by fitting the same model of MMRM as described for the endpoint of change from baseline of FVC at 26 weeks (mL) in addition to summary statistics by treatment.

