#### **2.6.1.3 Patient reported outcomes**

L-IPF (Impacts and Symptoms Modules), K-BILD, Leicester cough, and R-Scale for IPF questionnaires score will be reported by treatment group, patients, and epoch/visit/time. Summary statistics on the change from baseline of PRO score at the end of the treatment epoch will be provided by treatment and visit time. For continuous PRO endpoints, if data allows, the endpoints will be analyzed by fitting the same model of MMRM as described for the endpoint of change from baseline of FVC at 26 weeks (mL) in addition to summary statistics by treatment.

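### If the unstructured MMRM fails, the only named fallback is AR(1), whose single variance would make the week-26 standard error too small if the spread of FVC change grows over time

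*SAP*

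**What the plan says.** SAP 2.6.1.1 (Efficacy) analyses change in FVC (mL) with an MMRM. The mean model includes "treatment-by-visit and baseline-by-visit as interaction terms", so treatment means are free at each visit. Within-subject correlation is handled by a "repeated statement in SAS Proc Mixed with unstructured covariance matrix". On non-convergence, "an alternative AR(1) covariance may be implemented".

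The SAP does not name an intermediate structure, an order of fallbacks, a standard-error method or a degrees-of-freedom method.

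The model is reused. DLCO "will be analyzed by fitting the same model of MMRM", 6-minute walk distance is treated likewise, and for continuous PROs, if the data allow, "the endpoints will be analyzed by fitting the same model of MMRM". SAP 2.6.4 plans no sensitivity analysis for secondary endpoints.

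For the primary endpoint, Protocol 12.4.2 and SAP 2.5.2 use a model with "the intercept and slope of time for each participant as random effects". Protocol 12.5.1 had planned a similar model for FVC in mL and the same one for DLCO and walk distance.

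**The concern.** In Proc Mixed, AR(1) has a single residual variance for all visits; the version with visit-specific variances is a separate option, ARH(1). If participants decline at different rates, as the primary model assumes, their changes from baseline fan out and the variance is largest at the last visit. With free visit means and complete data, the week-26 contrast is a difference in baseline-adjusted means, so its standard error should come from the week-26 variance. AR(1) substitutes a variance pooled over visits, which is smaller.

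Week 26 is the time point of interest for these endpoints. Its intervals would be too narrow, and no other planned analysis of these endpoints would show it.

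**Working it through.** **The plan's own figures.** The documents give no standard error, alpha or by-visit SD for the MMRM. The nearest figure is for the primary endpoint, "assuming the standard deviation is around 5" percentage points (Protocol 12.8.1). Simulating the primary criterion with that SD, 40 per group, the Table 12-1 prior and one interim analysis gives 79.3% power at a difference of 2, against 79% in Table 17-5. SD 5 is therefore a fair scale. The ratios below do not depend on the unit.

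**Inputs.**
- 47 per arm and 15% dropout (Protocol 17.1.11.1).
- Visit days 29, 57, 85, 113, 141 and 183 (Table 8-1). That spirometry is done at all six is an assumption, because its row is not in the available text.
- Week-26 SD of 5.
- f, the share of week-26 variance that is measurement noise. The documents do not give it, so it is varied.

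**Assumed truth.** Let t = (day − 1)/182. With random slopes plus independent error at baseline and at each visit,

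Var(change at t) = 25 × [f + (1 − f)t²].

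For f = 0.50 at Day 29: t = 28/182 = 0.154, t² = 0.0237, SD = 5 × √(0.50 + 0.50 × 0.0237) = 3.58. At Day 183 it is 5.00.

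**Hand check, complete data.** The true SE is 5 × √(2/47) = 1.031. The six t² values are 0.024, 0.095, 0.213, 0.379, 0.592 and 1, with mean 0.384. If AR(1) simply averaged the variances,

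SE ratio ≈ √[f + (1 − f) × 0.384],

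which is 0.73, 0.83, 0.92 and 1.00 for f = 0.25, 0.50, 0.75 and 1.

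**Likelihood limit.** AR(1) fits the correlation jointly with the variance. Solving for the values to which the likelihood converges gives complete-data ratios of 0.753, 0.839, 0.922 and 1.000. With 15% dropout:

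| f | SD, Day 29 to Day 183 | True SE | AR(1) SE | Ratio | 95% coverage |
|---|---|---|---|---|---|
| 0.25 | 2.59 to 5.00 | 1.092 | 0.815 | 0.75 | 85.7% |
| 0.50 | 3.58 to 5.00 | 1.101 | 0.923 | 0.84 | 90.0% |
| 0.75 | 4.35 to 5.00 | 1.106 | 1.022 | 0.93 | 93.0% |
| 1.00 | 5.00 to 5.00 | 1.109 | 1.113 | 1.00 | 95.1% |

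Coverage is 2Φ(1.96 × ratio) − 1. For ratio 0.839, 1.96 × 0.839 = 1.644, which gives 90.0%. The 95% level is a yardstick, since the SAP sets none. At f = 0.10 the ratio is 0.69; at f = 0.90 it is 0.97.

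**REML simulation** (1,500 trials per f, 47 per arm, baseline-by-visit terms, 15% monotone dropout): ratios 0.74, 0.84, 0.93 and 1.02; coverage 85.1%, 89.7%, 93.3% and 94.8%. The Monte Carlo error of the lowest coverage is about √(0.85 × 0.15/1500) = 0.9 points.

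**Visit spacing.** The last gap is 183 − 141 = 42 days; the others are 28.
- Unequal spacing with constant variance: ratio 1.000 with complete data, 0.997 to 0.998 with dropout.
- Growth with equal spacing, with dropout: 0.76, 0.85 and 0.93 for f = 0.25, 0.50 and 0.75.
- A homogeneous structure using the actual days, with dropout: still 0.76 and 0.85 for f = 0.25 and 0.50.

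Variance growth therefore drives the result.

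**Alternatives.** Model-based ARH(1) gives 0.90 to 0.91 at f = 0.25 and 0.95 to 0.96 at f = 0.50, so it is still about 4% to 10% low. A sandwich standard error targets the true value.

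**The case against.** The strongest reply is that the problem depends on a chain of conditions. AR(1) is optional, arises only after non-convergence, and touches secondary endpoints in an exploratory trial that SAP 1.2.1 describes as non-registrational. The success criterion uses the Bayesian FVC percent-predicted model, which is unaffected. All of this stands and limits the weight of the point.

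It is also fair that variance growth is not documented. With small slope variance, or a negative covariance between intercept and slope, the spread could be almost flat, and the understatement would then largely vanish. The random-slope model is stated for FVC; for PROs the documents offer no similar evidence, and for DLCO and walk distance only the protocol's earlier choice of the same model. What remains is that a single variance sits badly with the trial's own view of FVC.

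Four stronger readings are tempting but not supported:
- **The uneven last gap is a second cause.** Alone it changes the standard error by at most 0.3%.
- **The SAP prescribes model-based errors.** It says only that "The within subject correlation will be modeled using a repeated statement in SAS Proc Mixed". Model-based errors are the software default, so the accurate statement is that no robust method is specified.
- **Early termination makes the fallback likely.** Six visits need 6 × 7/2 = 21 covariance parameters and 94 participants were planned, but the documents give neither the number enrolled at termination nor any convergence information.
- **Type I error is 10% to 15% for a nominal 5% test.** That is the result for noise shares of about 50% down to 25%. It is not a property of the plan, which sets no alpha for these models.

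**Conclusion.** The point holds as a minor, inexpensive improvement. If the unstructured fit fails, AR(1) is used with default errors and the variance of change grows, the week-26 standard error is too small: by about 25%, 16% and 7% to 8% when noise makes up 25%, 50% and 75% of the week-26 variance, and not at all without growth. These sizes assume six post-baseline visits, linear random slopes with independent error, and a week-26 SD of 5. The direction follows from the trial's own FVC model; the documents cannot settle the size. For DLCO, walk distance and continuous PROs, the point applies only where the same model is used and the variance also grows.

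**What to change.** In SAP 2.6.1.1, replace the AR(1) sentence with a fixed order that keeps visit-specific variances: unstructured; then heterogeneous Toeplitz; then heterogeneous compound symmetry or heterogeneous AR(1), stating which of the two is tried first. The first structure to converge is used. For any structure other than unstructured, use empirical (sandwich) standard errors and name the small-sample correction and the degrees-of-freedom method, after checking that they are available together in the procedure used. The sandwich step is needed because heterogeneous AR(1) alone does not remove the understatement. Apply the same rule to DLCO, walk distance and the PRO models by reference.

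The cost is one or two SAP sentences and a procedure option; no extra data are needed. The downside is that uncorrected sandwich errors are slightly liberal in small samples, which is why the correction should be named in advance. Fixing the order also removes the discretion left by an optional fallback.
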